8.4 Safety

8.4.1 Adverse Events

8.4.1.1 Definition of Adverse Event

The definitions below follow International Conference on Harmonization (ICH) – Good Clinical Practice (GCP) (see also ICH Guideline for Clinical Safety Data Management: Definitions and Standards for Expedited Reporting).

Adverse Event (AE)

An AE is defined as any untoward medical occurrence in a subject administered a pharmaceutical product and which does not necessarily have a causal relationship with this treatment. An AE can therefore be any unfavorable and unintended sign (including an abnormal laboratory finding), symptom, or disease temporally associated with the use of a medicinal (investigational) product, whether or not considered related to the medicinal (investigational) product.

Any clinically significant change in a condition (worsening) from screening that results in a change in subject management will be considered an AE and will be recorded on the AE page of the CRF.

By definition for this study, all untoward medical occurrences beginning on the day of Visit 1 Screening (Days -45 to -1) through the assessment of the Safety Follow-up Telephone Call (Day 8 ± 3) are to be reported as AEs. AEs continuing after study completion will be followed to normalization or stabilization. SAEs will be reported from the time of consent through the end of participation.

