8.4.1.3 Assessments and Documentation of Adverse Events

Attention shall be paid to the occurrence of AEs for the duration of subject participation. Untoward medical events beginning on Visit 1 Screening (Days -45 to -1) through the completion of the Follow-up Telephone Call will be reported as AEs. Thus, subjects should be closely observed by the investigator both during and after the evaluation.

Any AE (observed, volunteered, or elicited) should be recorded in detail in the source documentation.

The following information is required:

- The date and time of onset of any AE.
- The duration (the entire duration of an event or symptom, calculated from date of onset to date of end, if not recorded directly).
- The seriousness of the AE will be assessed by the investigator. If the investigator deems that an AE qualifies as an SAE, a special form provided by the sponsor should be completed and the event must be immediately reported to the sponsor. A definition of SAEs is provided in Section 8.4.1.5.
- The maximum intensity (mild, moderate, or severe).
- Whether drug treatment was administered for the event, any specific drug treatment must be documented.
- The relationship of the AE to the investigational product and to study conduct (for definitions, see above).

The **outcome** of the AE (resolved, resolved with sequelae, not resolved, unknown, death).

AEs will be coded according to an internationally recognized dictionary (Medical Dictionary for Regulatory Activities [MedDRA]).

Confidential Page 51 of 71

Clinical Study Protocol Number: NAV3-30

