9.2 Safety Variables

The primary variable for this study is whether a subject observes any noxious pharmacologic activity/adverse drug reaction (ADR) during their enrollment in the trial. This is a safety endpoint. The pharmacologic activity or ADR must be observed after the dose of Tc99m tilmanocept is administered.

NOTE: Adverse Drug Reaction

An ADR includes all noxious and unintended responses to a medicinal product related to any dose or dose regimen. The phrase "responses to a medicinal product" means that a casual relationship between a medicinal product and an AE is at least a reasonable possibility, i.e. the relationship cannot be ruled out.

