9.5.4 Analysis of Safety Variables

The number and percentage of subjects with any noxious pharmacologic activity or ADRs will be tabulated by dose group and overall.

All AEs will be observed for each subject from the time of signing of informed consent until exit from the study. A treatment emergent AE is defined as an AE whose start date is on or after the procedure date. If the procedure date and/or the AE start date are missing, the AE will be considered treatment emergent.

Prior to analysis, all AEs will be coded using the MedDRA coding dictionary. Based on these coded terms, treatment emergent AEs will be summarized by dose group and overall as follows:

- by system organ class and preferred terms
- by system organ class and preferred terms and relation to study drug
- by system organ class and preferred terms and severity

Observed and change from baseline vital sign parameters, ECG parameters and hematology, clinical chemistry and urinalysis parameters will be summarized using descriptive statistics (mean, median, standard deviation, minimum, maximum and range) at each time point by dose group and overall.

Other safety analyses will be described in the SAP for the study.

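### The treatment-emergent rule uses only the AE start date, so a pre-dose AE that worsens after dosing can be left out of the three treatment-emergent AE tables

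*Combined protocol and SAP*

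**What the plan says.** Section 9.5.4 gives the rule: "A treatment emergent AE is defined as an AE whose start date is on or after the procedure date". For incomplete dates it adds: "If the procedure date and/or the AE start date are missing, the AE will be considered treatment emergent". The procedure date is not tied to either sulfur colloid (Day 0) or tilmanocept (Day 3).

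The AE tables then follow: "treatment emergent AEs will be summarized by dose group and overall as follows". Three are listed, all by system organ class and preferred term: one plain, one with relation to study drug, one with severity.

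The primary table is separate: "The number and percentage of subjects with any noxious pharmacologic activity or ADRs will be tabulated by dose group and overall". Its timing condition is in section 9.2 and does not refer to the AE start date: "The pharmacologic activity or ADR must be observed after the dose of Tc99m tilmanocept is administered".

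AEs are collected from screening (Day -45 to -1) to the follow-up call on Day 8 ± 3. Section 8.4.1.3 asks for the onset date and time of each AE, one maximum intensity, and a duration "calculated from date of onset to date of end, if not recorded directly". Section 8.4.1.1 has a worsening clause: "Any clinically significant change in a condition (worsening) from screening that results in a change in subject management will be considered an AE".

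**The concern.** AE collection begins up to 45 days before sulfur colloid and 48 days before tilmanocept, so some AEs may already be open at dosing. A definition based on start date alone cannot recognise that such an event got worse after the injection. Only a maximum intensity is recorded and no date of severity change is listed, so the worsening cannot be recovered at analysis from a single record.

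Safety in NASH subjects is the primary objective. If a related worsening counts as an ADR in the primary table but is absent from the table of treatment-emergent AEs by relation, the report contradicts itself for that subject. In the other direction, an undated event that ended before either product was given is counted as treatment emergent, although neither product can have caused it.

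**Working it through.** The plan gives no figure to reproduce on this point; the sample size of 12 has no formula behind it. The check applies the written rule to example records, with the procedure date set first to Day 0 and then to Day 3. It then repeats this with two additions: an AE that worsens on or after the procedure date is treatment emergent (TE), and an AE whose known end date precedes it is not.

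| Example record | Rule as written | With both additions |
|---|---|---|
| 1. Starts Day -10, worsens Day 3, kept as one record | Not TE (either date) | TE (either date) |
| 2. Same worsening entered as a new AE starting Day 3 | TE (either date) | TE (either date) |
| 3. Start missing, ended Day -5 | TE (either date) | Not TE (either date) |
| 4. Start and end both missing | TE (either date) | TE (either date) |
| 5. Starts Day 1, ends Day 2 | TE if Day 0, not TE if Day 3 | Unchanged |

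Records 1 and 3 change class. Records 1 and 2 are the same clinical event, so whether it is tabulated depends on how the site enters it. Record 5 shows a related gap: until the procedure date is named, any AE starting on Day 1 or 2 has no fixed class.

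**Does the worsening clause in 8.4.1.1 close the gap?** Only in part. It applies when the worsening changes subject management. Section 8.4.1.2 grades severity by tolerability, discomfort and interference with usual activities, so an AE can move up a grade with no management change. Where the clause does apply, the document does not say whether the worsening receives its own record and onset date.

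**Which outputs are exposed?** The three TE tables. The ADR table follows 9.2, and the vital sign, ECG and laboratory summaries do not use TE status.

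**Size of one misclassified subject.** The change in a percentage is 100/n. The TE tables are by dose group and overall. From the dosing paths in 5.2, the completed groups are 2 at 8.0 mCi and 6 at 2.5 mCi, or 6 and 6, or a single group of 6.

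- n = 12: 100/12 = 8.3 points
- n = 8 (overall, on the path with groups of 2 and 6): 100/8 = 12.5 points
- n = 6: 100/6 = 16.7 points
- n = 2: 100/2 = 50 points

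**How often record 1 might arise.** The document gives no rates, so these are assumptions: 20–50% of subjects have a pre-dose AE, 30–50% of those are ongoing at dosing, and 10–20% of those worsen.

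- Low: 12 × 0.2 × 0.3 × 0.1 = 0.07 subjects
- High: 12 × 0.5 × 0.5 × 0.2 = 0.6 subjects

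**The case against.** A reader might infer that the rule removes drug-related worsening from every safety table. The document does not support that. The primary ADR table is not limited to TE AEs, and 9.2 asks only that the event be observed after tilmanocept, so a related worsening remains eligible there. The vital sign, ECG and laboratory summaries are likewise unaffected.

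It is also fair to say that 8.4.1.1, read with the requirement in 8.4.1.3 for an onset date and time for any AE, may mean that a management-changing worsening is a new AE with its own onset. It would then pass the rule. CRF completion instructions are in a separate document, and 9.5.4 leaves other safety analyses to a SAP; neither text is available here. This narrows the gap but does not close it: the entry convention is not stated, worsening without a management change is not covered, and the TE definition itself is given outright in 9.5.4 and not deferred.

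On missing dates, counting undated AEs is the cautious default in a safety study, and a required onset date and time should make them uncommon. That stands. It does not justify counting an event whose recorded end date shows it was over before dosing.

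It would be tempting to size the effect in cells of 3 NASH or 3 control subjects, or by confidence limits. The TE tables in 9.5.4 are not split by subject type (the Synopsis makes that split for the ADR count), and no confidence limits are planned for AE incidence.

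**Conclusion.** The concern holds in a limited form. A pre-dose AE that worsens after dosing can be omitted from the three TE tables when it is kept as one record with its original onset date, or when the worsening does not change management and so falls outside 8.4.1.1. Because the event can still be a primary ADR, the primary table and the table by relation can disagree for the same subject. The missing-date rule is a smaller fault in the direction of over-reporting.

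On the assumed rates, fewer than one of 12 subjects would be expected to be affected by missed worsening. The case for acting rests on the effect of a single misclassification in such small groups and on consistency between two tables that serve the primary objective. The classification of records 1 and 3 does not depend on which administration is the procedure date; that of AEs starting on Day 1 or 2 does.

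**What to change.** In 9.5.4, and in the SAP to match:

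- Define a treatment-emergent AE as one that starts, worsens in severity or becomes serious on or after a named administration. State whether that is sulfur colloid on Day 0 or tilmanocept on Day 3, or flag emergence against each.
- Have worsening after an administration entered as a new AE record with its own onset date and time. One line in the CRF completion instructions is enough.
- Treat an AE with a missing or partial start date as treatment emergent unless its partial date, its end date, or the visit at which it was first recorded shows onset before that administration with no later worsening.

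No new visits or assessments are needed. End dates are already expected for the duration calculation, and AE checks before administration are already scheduled on Day 0 and Day 3. The cost is a few sentences of text and a few split AE records.

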9.5.5 Handling Missing Values

The analysis of the primary efficacy variables will be carried out on the observed data, i.e., a complete case analysis.

9.5.6 Interim Analysis

There are no interim analyses planned for this study.

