5.2 Investigational Product Dosage and Administration

[figure not shown]
On Day 0, subjects will receive an on label 8.0 mCi dose of unfiltered Tc 99m sulfur colloid via IV administration. On Day 3, subjects will receive 200 μg tilmanocept via IV administration at the specified radiolabeled dose of Tc 99m. A single syringe will be used for each product and injected as a slow push into the IV. At the completion of each injection, a 10 cc sterile normal saline flush will be administered. The preferred site of IV placement will be the left or right antecubital vein. The final administered tilmanocept dose will be \pm 20% of the mass dose and radiolabel mCi dose assignment.

The first two enrolled subjects will be NASH subjects who will receive an 8.0 mCi radiolabel dose of Tc 99m tilmanocept. A review meeting will be held following completion of the first two subjects to evaluate tilmanocept safety and dose performance.

At the review (as diagrammed below):

- 1. If it is determined that a lower radiolabel dose of tilmanocept may produce images of better quality, three additional NASH subjects and three HCs will be injected and imaged with 200 µg of 2.5 mCi Tc 99m tilmanocept. After these six subjects have completed the trial, no additional subjects will be enrolled.
- 2. If the review shows no safety signals and acceptable quality of imaging, one additional NASH subject as well as three HCs will be injected and imaged with 200 μg of 8.0 mCi Tc 99m tilmanocept. Once a total of three NASH subjects and three HCs have completed the trial, a second review meeting will be held to compare results from NASH subjects to those of the HCs. If it is determined at the second review meeting that a lower radiolabel dose of tilmanocept may produce additional clinically meaningful results, 3 NASH subjects and 3 HCs will be dosed with 200 μg of 2.5 mCi Tc 99m tilmanocept. If it is determined that additional doses will not provide clinically meaningful results, the trial will be concluded.

Confidential Page 39 of 71

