9.5.3 Analysis of Efficacy Variables

Co-location of tilmanocept and sulfur colloid intrahepatic tessellation localization (Figure 7) will be assessed through frequency tables derived by creating virtual slices of the liver.. These scans will be false-colored and overlaid, matching landmarks (e.g. large blood vessels) for image registration. The resulting voxel colors will be classified as binding tilamanocept, binding sulfur colloid, or binding both. No formal hypothesis tests are planned. Frequency tables will created for individual subjects and overall.

The voxel radiation intensities will be used to create non-parametric density estimates of ^{99m}Tc gamma radiation intensities for both Tc 99m tilmanocept and Tc 99m sulfur colloid. Density estimates will be created for both individual subjects and for NASH subjects and healthy controls pooled separately.

[figure not shown]

Figure 7. Diagrmatic representation of anticipated tessellation

Complete analyses and details will be described in the Statistical Analysis Plan (SAP) for the study.

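### Section 9.5.6 denies any interim analysis although Section 5.2 plans data-dependent reviews that set the activity and the final N, and the intensity outputs are not split by the resulting dose groups

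*Combined protocol and SAP*

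**What the plan says.** Section 9.5.6 consists of one statement: "There are no interim analyses planned for this study".

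Section 5.2, repeated in the synopsis, sets out a branching design:

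- **First review.** Two NASH subjects receive 8.0 mCi. "A review meeting will be held following completion of the first two subjects to evaluate tilmanocept safety and dose performance".
- **Path 1.** If a lower activity may give better images, three NASH subjects and three controls receive 2.5 mCi. "After these six subjects have completed the trial, no additional subjects will be enrolled".
- **Path 2.** The other outcome reads: "If the review shows no safety signals and acceptable quality of imaging, one additional NASH subject as well as three HCs will be injected". The activity on this branch stays at 8.0 mCi. At three NASH subjects and three controls, "a second review meeting will be held to compare results from NASH subjects to those of the HCs".
- **Extension on path 2.** If that meeting finds that a lower activity "may produce additional clinically meaningful results, 3 NASH subjects and 3 HCs will be dosed with" 2.5 mCi.
- **Stop on path 2.** "If it is determined that additional doses will not provide clinically meaningful results, the trial will be concluded".

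Section 9.4 gives a single sample size of 12. The synopsis and Section 8.1.1 treat 12 (six per group) as a ceiling.

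On analysis, Section 9.5.3 plans per-subject and overall frequency tables of co-location, and density estimates of voxel intensity: "Density estimates will be created for both individual subjects and for NASH subjects and healthy controls pooled separately". It states that no formal hypothesis tests are planned. The synopsis summarizes localization intensities at each time point against controls. None of these outputs carries a dose split. By contrast, Section 9.5.4 tabulates adverse drug reactions by dose group and overall, and the synopsis gives reactions and localization rates by subject type, dose group and overall.

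**The concern.** An open-label between-group comparison of accrued data, scheduled in advance and feeding a decision to stop or go on, is an interim analysis whatever the meeting is called. Section 9.5.6 read alone gives the wrong account of how the data were seen and how N came about. No data cut, record of what was reviewed, or criterion on the NASH-control contrast is given for either meeting.

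The second issue follows from the first. The reviews create dose groups, and voxel intensity is the outcome most directly exposed to the administered activity. Summaries of intensity that ignore dose group can show a NASH-control difference, or an odd-shaped distribution, that comes from the mixture of activities and not from the liver.

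**Working it through.** **1. Final N by path** (cohort sizes from Section 5.2, no replacements counted)

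| Path | NASH | Controls | N |
|---|---|---|---|
| 1: lower activity after first review | 2 + 3 = 5 | 3 | 8 |
| 2: stop at second review | 2 + 1 = 3 | 3 | 6 |
| 2: extend at second review | 3 + 3 = 6 | 3 + 3 = 6 | 12 |

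The plan's figure of 12 is reproduced on the third row only. This matters for the primary safety endpoint. With no reactions observed, the exact two-sided 95% upper bound is 1 − 0.025^(1/N): 45.9% at N = 6, 36.9% at N = 8 and 26.5% at N = 12.

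**2. Activity mix in the unsplit intensity outputs**

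Assume that voxel intensity is proportional to administered activity, that uptake is identical in all subjects, and that no normalization is applied (Section 9.5.3 states none). The activity ratio is 8.0/2.5 = 3.2.

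- Path 1: two NASH subjects at 3.2 units and three at 1, with all controls at 1. The pooled NASH mean is (2 × 3.2 + 3 × 1)/5 = 9.4/5 = 1.88 times the control mean, with no disease difference.
- Path 2, extended: each group has three subjects at 3.2 and three at 1, a mean of (3 × 3.2 + 3 × 1)/6 = 2.1 in both. The contrast is not confounded, but each pooled density is a mixture of two activities.
- Path 2, stopped: one activity only, so there is no mixing.

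The proportionality assumption is rough. Section 8.2 sets a count target for planar scans and allows a shorter acquisition at higher activity, which would offset part of the ratio there.

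**3. Selection from the second review (illustration only)**

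Assumptions that are not in the documents: a single normal outcome with between-subject SD 1, one common true NASH-control difference at both activities, and extension when the first 3 vs 3 contrast exceeds a cut-off lying c standard errors from its true value.

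- SE of the 3 vs 3 contrast = √(1/3 + 1/3) = √(2/3) = 0.816 SD.
- Mean overstatement of that contrast, given extension = 0.816 × φ(c)/(1 − Φ(c)). At c = 0 this is 0.816 × 0.798 = 0.65 SD.
- With two equal stages the pooled 6 vs 6 contrast carries half: 0.33 SD at c = 0, 0.21 SD at c = −0.5 and 0.47 SD at c = +0.5.
- If a weak contrast triggers extension, the sign reverses.

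The stated criterion is different in kind: it asks whether a lower activity may add clinically meaningful results. These figures therefore show what selection of this kind could do, not what this plan would do.

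**The case against.** The reviews are not hidden. Both are set out in the synopsis and Section 5.2, and the first again in Sections 3.1 and 5.3. The first looks at two NASH subjects with no controls, so it is not a between-group look. The second exists only on path 2. In an open-label, non-randomized, descriptive phase 1 study, Section 9.5.6 may mean only that no formal inferential interim analysis is planned. Section 9.5.3 also leaves full details to a SAP, which could add the dose split. All of this stands, and it limits how serious the point is. It does not make the sentence in Section 9.5.6 agree with Section 5.2, and it does not supply the split in the text as written.

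A reader might infer four stronger things that the documents do not support.

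- *The whole analysis pools over stages as if N were fixed.* It does not. Reactions and localization rates are split by dose group, which on path 2 is the same as stage, and N is elsewhere given as a ceiling.
- *The pooled contrast is biased upward by a known amount.* No threshold on the contrast is stated, and the extension opens a cohort at a different activity. The 8.0 mCi comparison on path 2 is complete at 3 vs 3 whether or not the trial continues, so the second review cannot bias it if it is always reported.
- *The two looks inflate type I error.* No tests are planned, so there is no error rate to inflate.
- *No pooled figure should be shown at all.* That is a preference. Labelling and order of display are enough.

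**Conclusion.** The point holds in two parts.

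First, Section 9.5.6 is wrong as written and conflicts with Section 5.2 and the synopsis. Final N depends on the reviews (8, 6 or 12), and 12 is reached only if the second review extends the trial. This rests on the text alone.

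Second, the Section 9.5.3 density estimates and overall frequency tables and the synopsis intensity summaries have no dose split. They therefore mix activities on path 1 and on extended path 2, and on path 1 the NASH-control contrast is confounded with activity. The factor of 1.88 rests on proportional, unnormalized intensity; the confounding itself follows from the cohort plan.

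Selection bias in a cross-stage pooled figure is possible, but its size and direction cannot be determined from the documents. For a phase 1 feasibility study the importance is moderate to low, but the correction is cheap and should be made before the data are summarized.

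**What to change.** Reconcile Section 9.5.6 with Section 5.2. Suggested text: *Open-label, data-dependent, non-inferential reviews are planned as described in Section 5.2: one after two NASH subjects and, on path 2, a second that compares NASH with control results and may end the trial.* Keep the dated data cut and the tables seen at each review. In Section 9.4, give N as 8, 6 or 12 by path.

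In Section 9.5.3 and the synopsis, make subject type by dose group (stage) the main display for the density estimates, frequency tables and intensity summaries. On path 1 this separates the first two NASH subjects from the rest. Any figure pooled across stages should be secondary and, on path 2, labelled as following a data-dependent extension.

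The cost is wording and a few extra table columns, with no added subjects and no change to the dosing plan. The downside is that dose-group results rest on about 3 vs 3 and will look less precise than a pooled 6 vs 6.
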